2.5.3 Handling of missing values/censoring/discontinuations

Patients with unknown or missing best overall response (BOR) will be counted as failures, i.e. non-responders. Patients who were non-responders before initiation of subsequent anti-cancer therapy will still be non-responders. If there is no baseline tumor assessment, all post-baseline overall lesion responses are expected to be 'Unknown'. If no valid post-baseline tumor assessments are available, the best overall response must be "Unknown" unless progression is reported. For the computation of ORR, these patients will be included in the FAS and will be counted as 'failures'.

2.5.4 Supportive analyses

As a supportive analysis, ORR based on RECIST v1.1 criteria as per blinded independent central review (BICR) will be analyzed with the same analysis conventions as the primary efficacy analysis, and the treatment effect will be summarized by the ORR with its 95% confidence interval using the Clopper-Pearson method.

Subgroup analyses for the primary endpoint

The primary endpoint of ORR will be summarized for the subgroups specified in [Section 2.2.1](#) based on the primary analysis source (i.e., investigator assessment) and the same conventions as for the primary analysis. For each of the subgroups, the proportion of patients with objective response will be analyzed.

Forest plot (n, odds ratio, 95% CI) will be produced to graphically depict the treatment effect estimates in different subgroups. No inferential statistics (p-values) will be produced for the subgroups.

Concordance analysis of BOR

An assessment of the concordance between BIRC assessment and local assessment of the Best Overall Response for each subject will be provided by treatment arm. The calculation will be based on the percent agreement (the proportion of response outcomes that agree or match across both Independent Reviewer and Investigator Assessments):

$$\text{Percent Agreement} = \frac{\text{Number of matched responders} + \text{Number of matched non - responders}}{\text{Total Numbers of subjects assessed}}$$

Reasons for “Unknown” BOR

Patients with ‘unknown’ BOR will be summarized by reason for having unknown status. The following reasons will be used:

- No valid post-baseline assessment
- All post-baseline assessments have overall lesion response UNK
- New anti-neoplastic therapy started before first post-baseline assessment
- SD or non-CR/non-PD too early
- PD too late

Note 1: A SD or Non-CR/Non-PD is considered as “SD too early” if the SD or Non-CR/Non-PD is documented within first 11 weeks (takes into account the 1 week window for post-baseline assessments) after randomization date.

Note 2: A PD is considered as “PD too late” if the first documentation of PD is recorded more than 13 weeks after randomization date (takes into account the 1 week window for post-baseline assessments) with no qualifying CR, PR or SD or Non-CR/Non-PD in between.

Note 3: Special (and rare) cases where BOR is “unknown” due to both too early SD and too late PD will be classified as “SD too early”.

Waterfall plot to depict anti-tumor activity

Waterfall graphs will be used to depict the anti-tumor activity based on local and central assessment separately. These plots will display the best percentage change from baseline in the sum of diameters of all target lesions for each patient. Only patients with measurable disease at baseline will be included in the waterfall graphs. Special consideration is needed for assessments where the target lesion response is CR, PR or SD, but the appearance of a new lesion or a worsening of non-target lesions results in an overall lesion response of PD. As a conservative approach, such assessments will not be considered for display as bars in the graph, since the percentage change in the sum of diameters of target lesions reflects the non-PD target lesion response, but the overall lesion response is PD. A patient with only such assessments will be represented by a special symbol (e.g. ★) in the waterfall graph. Assessments with “unknown” target lesion response and assessments with unknown overall response will be excluded from the waterfall plots. Patients without any valid assessments will be completely excluded from the graphs.

The total number of patients displayed in the graph will be shown and this number will be used as the denominator for calculating the percentages of patients with tumor shrinkage and tumor growth. Footnote will explain the reason for excluding some patients (due to absence of any valid assessment).

All possible assessment scenarios are described in [Table 2-12](#).

Table 2-12 Inclusion/exclusion of assessments used in waterfall graph

	Criteria for inclusion/exclusion	Possible sources of contradictions
--	----------------------------------	------------------------------------

case	Target response	Overall lesion	Include in waterfall?	Non-target	New lesion?
1	CR/PR/SD	PD	Yes but as " only	PD	any
2	CR/PR/SD	PD	Yes but as " only	any	Yes
3	UNK	UNK or PD	No	any	any
4	CR/PR/SD	UNK	No	UNK	No
5	CR/PR/SD	CR/PR/SD	Yes as a bar	SD/IR	No
6	PD	PD	Yes as a bar	any	any

Percentage change from baseline in the sum of diameters of all target lesions over the time will be displayed for individual patients per combination arm.

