No formal comparisons will be made between the combination arms for ORR in this ‘selection’ phase; instead each of the arms will be evaluated against efficacy and futility thresholds as presented above.

The final decision on whether an arm will be selected for advancement to the expansion phase will primarily be based on the observed ORR using decision rule described above but other efficacy (in particular duration of response), safety, and biomarker data will be considered as well. Further considerations related to the design and execution of the selection phase will be captured in the [\[SAP Technical Appendix\]](#).

Part 2: Expansion Phase

For the arms which show promise for efficacy in part 1 (based on pre-defined criteria), these arms will be expanded. After completion of the expansion phase and within each arm separately, the following statistical hypothesis will be tested based on objective response rate (ORR):

- The null hypothesis is that the response rate is not clinically meaningful ($\leq 10\%$).
- The alternative hypothesis is that the response rate is clinically meaningful ($>10\%$). The target response rate that warrants further development is $\geq 25\%$

The null hypothesis will be formally rejected if the lower bound of exact 95% CI for ORR is above 10%. **The primary analysis of ORR at the end of part 2 will be based on a combined pool of part 1 and part 2 data for any given arm.**

For example, assuming 24 subjects enrolled in an arm of interest in part 1 (see Section 10.8 of the protocol for details), assuming this arm met criteria for expansion and finally assuming 50 subjects are enrolled in the expansion phase, then combined among 74 subjects enrolled in this arm in total and followed sufficiently, 14 or more responses need to be observed to reject the null hypothesis. With those 14 responders among 74 subjects, the point estimate for ORR will be 18.9% with an exact 95% confidence interval of (10.8%, 29.7%). Since the lower bound of the exact 95% CI will be $> 10\%$, this leads to rejection of null hypothesis. The exact 95% CIs for potential observed ORR in 74 subjects are shown in [Table 2-10](#):

Table 2-10 **Exact binomial 95% confidence intervals around potential observed ORR for N=74**

Number of responders	Observed ORR (%)	95% exact CI (%)
10	13.5	6.7, 23.5
11	14.9	7.7, 25.0
12	16.2	8.7, 26.6
13	17.6	9.7, 28.2
14	18.9	10.8, 29.7

Number of responders	Observed ORR (%)	95% exact CI (%)
15	20.3	11.8, 31.2
16	21.6	12.9, 32.7

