2.2.1 Subgroup of interest

Subgroup analysis as described in the main SAP for the randomized part of the study may be only performed at the primary analysis (e.g. once all patients from part 2 have been enrolled and followed for at least 9 months) but not at interim analyses. Of note, LDH subgroup defined in the main SAP for the randomized part of the study as a stratification factor is not a stratification factor for this non-randomized section of the study. In addition, subgroup linked to ECOG performance status will be defined as 0 versus 1.

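### In the ORR subgroup analysis, the forest plot calls for odds ratios although there is no reference group, and the ECOG groups (0 vs ≥0) overlap

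*SAP*

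**What the plan says.** The main SAP describes the ORR subgroup analysis in two places.

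- **Section 2.2.1** lists LDH and BRAF V600 status for all arms. For an expanded arm it adds age, ECOG PS and PD-L1 as optional subgroups, using only the patients of that arm. The ECOG split is written as 0 vs ≥0. The section promises a point estimate and 95% CI without tests, and refers to Sections 2.5.2 and 5.4.1 for the method. Its stated aims are to show homogeneity and to find subgroups in which efficacy differs.
- **Section 2.5.4** applies the primary-analysis conventions to each subgroup and says "For each of the subgroups, the proportion of patients with objective response will be analyzed". The next paragraph then says "Forest plot (n, odds ratio, 95% CI) will be produced to graphically depict the treatment effect estimates in different subgroups", with no p-values. Earlier in the same section, for the central-review ORR, "the treatment effect will be summarized by the ORR with its 95% confidence interval using the Clopper-Pearson method".

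The inferential frame is in Section 2.5.2. For part 1, "No formal comparisons will be made between the combination arms for ORR in this" selection phase. For part 2, "within each arm separately, the following statistical hypothesis will be tested based on objective response rate (ORR"), and "The null hypothesis will be formally rejected if the lower bound of exact 95% CI for ORR is above 10"%. Section 5.4.1 carries this out as a single-arm exact binomial test against 0.10.

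The Arm 1A SAP takes over the main SAP's subgroup analysis for a non-randomized single arm, but changes one split: "subgroup linked to ECOG performance status will be defined as 0 versus 1".

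**The concern.** A forest plot of odds ratios labelled as treatment effects belongs to a controlled comparison, where each row contrasts treated and control patients within a subgroup. Here each row would hold patients of one arm who all receive the same combination. Whoever programs the figure would have to choose a contrast that the plan does not name, possibly after seeing the data. If the choice fell on one subgroup level against another, readers would see an association with response under a treatment-effect label.

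The ECOG split is a separate slip. Every patient satisfies ECOG ≥0, so ECOG 0 patients are counted in both groups. The contrast is pulled towards no difference, which works against the stated aim of finding differential efficacy.

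**Working it through.** **1. The plan's own effect measure.** Section 2.5.2 gives 14 responders of 74 as 18.9% with exact 95% CI (10.8%, 29.7%). Recomputing the Clopper-Pearson interval gives 18.9% (10.7%, 29.7%), so the lower limit agrees to within 0.1 point. For 13 of 74 the result is 17.6% (9.7%, 28.2%), so 14 is the smallest count that rejects, as stated. The measure needs responders and patients from one arm and nothing else.

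**2. What an odds ratio needs.** For a treatment effect within a subgroup, OR = (a/b)/(c/d), with a responders and b non-responders on treatment, and c and d the same counts in a reference group.

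| Where | What it supplies |
|---|---|
| 2.5.2, part 1 | No formal comparison between arms |
| 2.5.2, part 2 | One arm against a fixed 10% |
| 5.4.1 | Single-arm exact binomial; no odds ratio model or reference category |
| 2.2.1, age, ECOG, PD-L1 | Patients of one expanded arm only |
| Arm 1A SAP | One non-randomized arm; null rate 15% |

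None of these supplies c and d.

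**3. What could be computed instead.** The SAP gives no subgroup counts, so assume 74 patients, 14 responders, 44 patients with ECOG 0 (about 60%) and 10 of the 14 responders among them. Then ECOG 0 has 10 responders and 34 non-responders, and ECOG ≥1 has 4 and 26. The level-versus-level odds ratio is (10 × 26)/(34 × 4) = 260/136 = 1.91. All 74 patients have the same treatment, so the 1.91 describes ECOG and response, not treatment.

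The planned measure works directly on the same counts: 10/44 = 22.7% (11.5%, 37.8%) and 4/30 = 13.3% (3.8%, 30.7%).

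**4. The ECOG overlap.** Let w be the share with ECOG 0, p0 their ORR and p1 the ORR of the rest. The ≥0 group has ORR w·p0 + (1 − w)·p1, so

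displayed gap = p0 − [w·p0 + (1 − w)·p1] = (1 − w)(p0 − p1).

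Assume w = 0.6, p0 = 30% and p1 = 10%. The ≥0 group shows 0.6 × 30 + 0.4 × 10 = 22%, a gap of 30 − 22 = 8 points instead of 20. With w = 0.5 the gap is 0.5 × 20 = 10 points; with w = 0.7 it is 0.3 × 20 = 6 points.

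The counts in step 3 agree: 22.7 − 18.9 = 3.8 points displayed against 22.7 − 13.3 = 9.4 points, and 9.4 × 30/74 = 3.8.

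The group sizes also fail to add up. With 37, 44 or 52 of 74 patients at ECOG 0 (shares of about 50%, 60% and 70%), the two groups sum to 111, 118 or 126 instead of 74.

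**The case against.** The strongest defence is that the analysis is already specified correctly around the faulty sentence. Sections 2.2.1, 2.5.1, 2.5.4 and 5.4.1 together call for the ORR with an exact CI in each subgroup, and Section 2.5.4 itself uses treatment effect to mean the ORR. The odds ratio then looks like leftover template wording. Table 2-13, which mentions crossover from a control arm that this study lacks, points the same way, though that is an inference. ECOG 0 vs ≥0 is very likely a typing error. The analyses are descriptive, and the ECOG one is optional and depends on expansion and on patient numbers.

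Most of this stands, and it limits the point. A reader might infer that the subgroup analysis as a whole cannot be done. It can: LDH, BRAF, age and PD-L1 are properly defined, and their ORRs and intervals need nothing further. A reader might also infer that an arm-versus-arm odds ratio would contradict the no-comparison statement. That statement covers formal comparisons in the selection phase, so a descriptive odds ratio would not strictly breach it. The firmer ground is that no reference group is named and that part 2 is tested within each arm. Nor is every odds ratio uncomputable, as the level-versus-level example shows.

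The defence does not remove the two errors. The figure's statistic is stated explicitly and conflicts with the sentences around it. The ECOG split is corrected only in the Arm 1A SAP, so the randomized arms keep the overlapping definition.

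**Conclusion.** Two elements are wrong as written. The forest plot names a statistic that is undefined as a treatment effect in this design. The main SAP's ECOG subgroup sets one group against the whole arm. The first has no numerical size because no contrast is specified. The second multiplies the true ORR gap by the share of patients with non-zero ECOG. That factor is exact, but the 8-versus-20-point example and its range rest on assumed ECOG shares and response rates that the SAP does not give, and on the definition being programmed literally.

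The consequence is confined to descriptive subgroup displays. A reader might take the point as casting doubt on the main efficacy conclusion. The documents do not support that: the primary ORR test, its error control, the sample size and the expansion rules do not use these displays.

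**What to change.** - **Main SAP, Section 2.5.4:** replace the bracketed n, odds ratio and 95% CI with n, number of responders, ORR and exact Clopper-Pearson 95% CI for each subgroup level within each arm. No reference line at 10% is needed. It would invite reading each interval as a test, which Section 2.2.1 disclaims, and it would be the wrong rate for Arm 1A, where the null is 15%.
- **Main SAP, Section 2.2.1:** define the ECOG subgroup as 0 vs ≥1, so that the groups are disjoint and in line with the Arm 1A SAP.

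The cost is two wording edits and one figure shell. The methods are already in the SAP, and no additional data are needed.

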2.6 Analysis of the key secondary objective

The key secondary objective of the study is to determine duration of response treatment with spartalizumab in combination with novel agents in patients with previously treated unresectable or metastatic melanoma.

2.6.1 Key secondary endpoint

The key secondary endpoint of the study is DoR, defined as the time from the date of first documented response of CR or PR (i.e., the start date of response, not the date when response was confirmed) to the date of the first documented progression or death due to underlying cancer. For the key secondary efficacy analysis, DoR will be based on local investigators review of tumor assessments and using RECIST 1.1 criteria (see Appendix 2 of the protocol). The key secondary analysis will be based on FAS and will include all data observed up-to the cut-off date. As a supportive analysis, DoR will also be summarized based on the BIRC review of tumor data.

If a subject has not had an event before leaving study or initiation of subsequent anti-cancer therapy, progression-free survival is censored at the date of last adequate tumor assessment. Censoring of subjects who have not had an event before initiation of subsequent anti-cancer therapy corresponds to option F(2) presented in Table 14-9 of the protocol and is used in this study in order to obtain DoR estimates that are not confounded by subsequent therapies.

Discontinuation due to disease progression (collected on the 'End of treatment' and 'End of post treatment follow up' disposition pages) without supporting objective evidence satisfying progression criteria per RECIST 1.1 will not be considered disease progression for DoR derivation. Clinical deterioration will not be considered as a qualifying event for progression for the key secondary analysis.

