2.6.3 Handling of missing values/censoring/discontinuations

DoR will be censored at the date of the last adequate tumor assessment if no DoR event is observed prior to the analysis cut-off date or before the start of the new anticancer therapy date, whichever is earlier.

The date of last adequate tumor assessment is the date of the last tumor assessment with overall lesion response of CR, PR or SD before an event or a censoring reason occurred. In this case the last tumor evaluation date at that assessment will be used. If no post-baseline assessments are available (before an event or a censoring reason occurred) then the date of randomization/start date of treatment will be used.

In particular, DoR will be censored at the last adequate tumor assessment if one of the following occurs: absence of event; the event occurred after two or more missing tumor assessments; before the start of the new anti-cancer therapy. The term “missing adequate tumor assessment” is defined as a tumor assessment (TA) not performed or tumor assessment with overall lesion response of “UNK”. The rule to determine number of missing TAs is based on the time interval between the date of last adequate tumor assessment and the date of an event. If the interval is greater than twice the protocol-specified interval between the TAs and 2 times the protocol-allowed time window around assessments, then the number of missing assessments will be 2 or more.

Refer to [Table 2-13](#) for censoring and event date options and outcomes for DoR and PFS analysis (PFS analysis is further discussed in [Section 2-7](#)).

Table 2-13 Outcome and event/censor dates for DoR and PFS analysis

[figure not shown]
Situation	Date	Outcome
No baseline assessment	Date of randomization	Censored
Progression or death at or before next scheduled Assessment	Date of progression (or death)	Progressed
Progression or death after exactly one missing assessment	Date of progression (or death)	Progressed
Progression or death after two or more missing assessments	Date of last adequate assessment prior to missed assessment	Censored
No progression (or death)	Date of last adequate assessment	Censored
Treatment discontinuation due to 'Disease progression' without documented progression, i.e. clinical progression based on investigator claim	Date of last adequate assessment	Censored

Situation	Date	Outcome

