New anticancer therapy given prior to protocol defined progression (including patients who crossover from the control to the treatment arm.)	Date of last adequate assessment on or prior to starting new anti-cancer therapy (or crossover treatment)	Censored
Death before first PD assessment	Date of death	Progressed

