2.7.1 Secondary [REDACTED] efficacy endpoints

Progression-Free Survival (PFS)

PFS is defined as the time from the date of randomization to the date of the first documented progression or death due to any cause. PFS will be based on both local investigator and central assessments of tumor assessments and using RECIST 1.1 criteria (see Appendix 2 of the protocol). The primary analysis will be based on FAS and will include all data observed up-to the cut-off date. PFS will be censored at the date of the last adequate tumor assessment if no PFS event is observed prior to the analysis cut-off date or before the start of the new anticancer therapy date, whichever is earlier. (See [Table 2-4 Subject Table 2-13](#) and [Section 2.7.3](#) for additional details regarding censoring rules and determination of date of last adequate tumor assessment). Discontinuation due to disease progression (collected on the ‘End of treatment’ and ‘End of post treatment follow up’ disposition pages) without supporting objective evidence satisfying progression criteria per RECIST 1.1 will not be considered disease progression for PFS derivation. Clinical deterioration will not be considered as a qualifying event for progression.

[figure not shown]
Disease Control Rate (DCR)

DCR is defined as the proportion of patients with a best overall response (BOR) of confirmed CR or PR, or SD lasting 12 weeks or longer, according to RECIST 1.1 criteria. A patient will be considered to have SD for 12 weeks or longer if a SD response is recorded at 11 weeks or later from randomization, allowing for the ± 1 week visit window for tumor assessments. DCR will be calculated using the FAS based on both the local investigator and central tumor assessments.

Overall Survival (OS)

Overall Survival (OS) is defined as the time from date of randomization to date of death due to any cause. A cut-off date will be established for each analysis of OS. All deaths occurring on or before the cut-off date in the FAS will be used in the OS analysis.

If a patient is not known to have died at the time of analysis cut-off, OS will be censored at the date of last contact.

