2.6.1 Key secondary endpoint

For information on the key secondary endpoint, see the main SAP for the randomized part of the study. Note, due to small sample size at 1st interim analysis, only listings will be generated for DoR.

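### The duration of response (DoR) definition counts only cancer deaths, the event table it relies on has no cause restriction, and the SAP does not say which governs

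*SAP*

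**What the plan says.** Main SAP, Section 2.6.1: DoR runs from the first documented CR or PR "to the date of the first documented progression or death due to underlying cancer".

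Main SAP, Section 2.6.3: "DoR will be censored at the date of the last adequate tumor assessment if no DoR event is observed" by the cut-off or before new anticancer therapy. The section then refers to Table 2-13, titled "Outcome and event/censor dates for DoR and PFS analysis". Its rows include "Progression or death at or before next scheduled Assessment", a similar row for exactly one missed assessment, and "Death before first PD assessment". Each has the outcome of progressed, dated at progression or death, and none mentions cause. A death after two or more missed assessments is censored.

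Main SAP, Section 2.7.1: PFS, which uses the same table, ends at "first documented progression or death due to any cause".

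Arm 1A SAP, Section 2.6.1: "For information on the key secondary endpoint, see the main SAP for the randomized part of the study". Its Sections 2.6.2 and 2.6.3 refer back in the same way for method and censoring.

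**The concern.** Take a responder who dies of treatment toxicity while still in response, with assessments up to date. Under Table 2-13 this is a DoR event on the date of death. Under Section 2.6.1 it is not a DoR event, so the no-event rule in Section 2.6.3 censors the patient at the last adequate assessment. Two programmers could each follow the SAP and produce different DoR datasets. If the rule is left open until data are reviewed, it could be chosen with the deaths already known.

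The Section 2.6.1 reading has two further consequences. Kaplan-Meier then treats a patient who has died as someone whose response might have continued. The endpoint also comes to depend on attributed cause of death. The only such classification the SAP describes (Section 2.8.2, study indication or other) is selected by the investigator, and the study is open-label.

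DoR is the key secondary endpoint, and Section 2.5.2 names it among the data considered when an arm is advanced to part 2.

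**Working it through.** **No figure to reproduce.** The SAP gives no target, assumed median, event count or power for DoR. The check is a comparison of the rules, followed by illustrations on assumed inputs.

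**The rules side by side**, for a death in response with no missed assessments and no new therapy:

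| Cause of death | Section 2.6.1 with the no-event rule of 2.6.3 | Table 2-13 as written | PFS, Section 2.7.1 |
|---|---|---|---|
| Underlying cancer | Event | Event | Event |
| Toxicity or other | Censored at last adequate assessment | Event | Event |

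The conflict is confined to the second row. No sentence in the SAP says that deaths from other causes are censored. That follows from combining the definition with the no-event rule.

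**Direction.** Turning a death into a censoring removes the drop at the death date, so from that date onward the Kaplan-Meier estimate is higher or unchanged. Because censoring is back-dated, the patient also leaves the risk set early. If another responder has an event between the last adequate assessment and the death, the curve can be slightly lower within that gap only.

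**Illustration 1: constant hazards (assumed).** Let the median to progression or cancer death be 12 months, so λ = ln 2 / 12 = 0.05776 per month, and let h be the monthly hazard of non-cancer death. Censoring those deaths reports S(12) = exp(−12λ) = 50% and a median of 12 months. Counting them gives S(12) = exp(−12(λ + h)) and a median of ln 2 / (λ + h). Their share of all events is s = h / (λ + h).

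| h per month | λ + h | 12-month DoR, any death | Median, any death (months) | s |
|---|---|---|---|---|
| 0 | 0.05776 | 50% | 12.0 | 0% |
| 0.5% | 0.06276 | 47% | 11.0 | 8% |
| 1% | 0.06776 | 44% | 10.2 | 15% |
| 2% | 0.07776 | 39% | 8.9 | 26% |

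In this model the reported median equals the any-death median divided by (1 − s). For s = 5%, 10% and 20% the overstatement is 5%, 11% and 25%; an any-death median of 6 months would be reported as 6.3, 6.7 and 7.5. If s = 0 the two definitions agree.

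**Illustration 2: 14 hypothetical responders.** Fourteen is the number in the Section 2.5.2 example (14 of 74). The times are invented: events at 2, 3, 4, 5, 5.5, 6.5, 7, 8 and 9 months, and censoring at 10, 11, 12.5, 13 and 14.

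- All deaths counted: S(6) = 9/14 = 64.3%, median 7.0 months.
- Death at month 4 censored at month 3: S(6) = (12/14) × (9/11) = 70.1%, median 8.0.
- Deaths at months 3 and 4 censored at months 2 and 3: S(6) = (13/14) × (9/11) = 76.0%, median 9.0.

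**Against sampling error.** With 14 responders and no censoring, a 50% estimate has standard error √(0.5 × 0.5 / 14) = 13.4 points, or about ±26 points at 95%. The 3 to 11 point shift in Illustration 1 lies inside that.

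**The case against.** The best defence is that Table 2-13 only assigns dates and censoring, and that death in it means a death qualifying under each endpoint's own definition. The table does look like a generic PFS template. One row covers crossover from a control arm, although Section 1.1 forbids crossover; another covers a missing baseline assessment, which cannot apply to a responder. It is therefore weak evidence of what was intended for DoR. This stands, but the SAP does not state that reading, and Section 2.6.1 gives no reason for restricting deaths by cause although it does explain its censoring at new therapy.

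A reader might infer that the DoR results will be inflated. The documents do not support that: the bias arises only if Section 2.6.1 is programmed, and its size depends on non-cancer deaths among responders, which are not given.

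A reader might also infer that expansion decisions or the primary test are compromised. Section 2.6.2 plans no hypothesis test on DoR. Expansion rests primarily on observed ORR (Section 2.5.2 of both plans), and at the first Arm 1A interim DoR is only listed. Nor would fatal toxicity be hidden: PFS and OS count deaths from any cause, and Section 2.8.2 summarises and lists deaths.

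Finally, the cancer-death wording may come from the protocol, which is not at hand. Section 4 does not list DoR among the changes from it, so an SAP-only edit could create a difference. That is a fair caution about how to make the fix.

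**Conclusion.** The point holds as an unresolved conflict between the DoR definition in Section 2.6.1 and Table 2-13, inherited by Arm 1A. The consequence is conditional: under Section 2.6.1, non-cancer deaths in responders are censored and the Kaplan-Meier estimate is raised or unchanged from each such death onward; under Table 2-13 as written, this does not happen.

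Under the assumed constant hazards, a reported 12-month DoR of 50% corresponds to 47% to 39% counting every death, with non-cancer deaths making up 8% to 26% of events. These inputs come from outside the documents, and the figures show scale only. The conflict should be fixed before database lock. It affects a descriptive endpoint and leaves the ORR test and its error rate untouched.

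**What to change.** - In Section 2.6.1, change the death component of DoR to death from any cause, in line with Table 2-13 and the PFS definition. Arm 1A follows by reference.
- In the same section, the censoring sentence names progression-free survival as the quantity being censored. It should name DoR.
- Check the definition against the protocol and record any difference in Section 4.
- If a cancer-death-only DoR is of interest, keep it as a labelled sensitivity analysis and state which cause-of-death field defines it.

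The cost is SAP wording and one derivation line, plus a Section 4 entry if the protocol differs. Reported DoR may be slightly shorter.
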